## **DATA COLLECTION**

A team properly instructed will collect patient's data, which will be filled in a CRF (Case Report Form). An electronic copy of CRF will be retained in Microsoft Excel format.

All collected data will be identified and stored in such a way as to protect patient confidentiality. The staff involved in the collection and management of data will not use or disseminate such information for purposes other than those provided for the realization of the study.

All data will be collected and processed in a completely anonymous way, in compliance with the guarantee terms of privacy and as approved by Comitato Etico per la Sperimentazione Clinica della Provincia di Padova.

### **Assessment of renal function**

“Acute kidney injury” (AKI) is defined as an increase in serum creatinine (SCr) by  $\geq 0.3$  mg/dL within 48 h the baseline value (as determined by all available SCr values from hospital and outpatient medical records within the previous 90 days) or urine output  $< 0.5$  mL/kg/h for 6 h. For those who do not have available baseline SCr levels, expand the screening criteria to an increase or decrease in SCr by 0.3 mg/dl during hospital stay. Second, these suspected AKI were reviewed on a case-by-case basis to confirm the diagnosis. Positive fluid balance and hemodilution are considered in the diagnosis and staging of AKI using the following formula:

Adjusted SCr level = SCr  $\times$  correction factor

where the correction factor = (weight (kg) upon hospital admission  $\times$  0.6 +  $\Sigma$  (daily cumulative fluid balance (L)))/hospital admission weight  $\times$  0.6

The estimated glomerular filtration rate is determined using SCr. Chronic Kidney Disease-Epidemiology Collaboration equations.

Persistent acute kidney injury (AKI) is defined by the continuance of AKI by serum creatinine or urine output criteria (according KDIGO criteria) beyond 48 h from AKI onset. Complete reversal of AKI by KDIGO criteria within 48 h of AKI onset is defined transient AKI.

Acute kidney disease (AKD) is defined as a condition wherein criteria for AKI stage 1 or greater persists  $\geq 7$  days after surgery.

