## **STUDY DESIGN**

Retrospective study

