**POSTOP :**

	6h	12h	24h	48h	72h	4d	5d	6d	7d	ICU discharge	H discharge	30d	1y
sCr													
eGFR													
urea													
Troponin													
BNP													
Hb													
NGAL													
diuresis													
Fluids in													
drainages													
diuretics													
vasopressors													
inotropes													

\*NA if not present in the medical records

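### For patients without a baseline creatinine, AKI is confirmed by a case-by-case review that is not limited to renal data, so knowledge of later outcomes could influence the label; the effect is probably small

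*Combined protocol and SAP*

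**What the plan says.** The section on assessment of renal function first gives a numeric rule. AKI "is defined as an increase in serum creatinine (SCr) by" at least 0.3 mg/dL within 48 h of the baseline value, or a urine output below 0.5 mL/kg/h for 6 h. Baseline comes from hospital or outpatient values in the previous 90 days.

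For patients with no baseline value, the same section tells the team to "expand the screening criteria to an increase or decrease in SCr by 0.3 mg/dl during hospital stay". The next sentence reads: "Second, these suspected AKI were reviewed on a case-by-case basis to confirm the diagnosis".

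Four other places bear on this:

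- Study design: "Retrospective study".
- Data collection: "A team properly instructed will collect" the data and enter them in the CRF. No separation of tasks is described.
- Case report form: the postoperative table holds creatinine, diuresis and fluids. The pages after it hold cardiac, pulmonary and surgical complications, the complication grade and death. The source is the chart, since items are to be marked "NA if not present in the medical records".
- Secondary endpoints: AKI is to be related to pulmonary, cardiovascular, anastomotic and septic complications and to death.

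The statistical analysis section plans no analysis that leaves out patients classified by the review.

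**The concern.** AKI status is the primary endpoint and also the exposure in the association endpoints. For most patients a numeric rule fixes it. For patients who reach the review, judgement enters. The screen works in both directions and covers the whole stay, whereas the primary endpoint concerns the first 48 hours. Someone must decide whether a fall of 0.3 mg/dL is recovery from AKI or something else, and when the injury began. No written rule settles either question.

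In a retrospective study, the complications and deaths have already happened when that decision is made. Nothing in the plan keeps them from the person deciding. If a doubtful case is confirmed more readily (or less readily) because the patient did badly, the exposure is misclassified in a way that depends on the outcome. Covariate adjustment does not repair that. Without a flag for these patients, a reader of the results could not tell whether it mattered.

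**Working it through.** **Which patients are reviewed.** The sentence on case-by-case review directly follows the one on patients without a baseline. Those patients are the natural reading, although the words could cover every suspected case. The documents do not say how many patients lack a baseline.

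**What the plan gives for scale.** The plan has no figure for this point. Its only planning figure is the event count in the sample size section: 8 events per covariate × 8 covariates = 64, which reproduces. At the 18.3% AKI incidence cited in the introduction, 64 / 0.183 = 349.7, or about 350 patients. That sets the size of the illustration.

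**Assumptions not in the documents.** 80 suspected cases; 30% complications in everyone, so no true association; unreviewed suspected cases all count as AKI; reviewed cases are confirmed in 80% of those with a complication and 40% of those without.

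**Twenty of the 80 reviewed.**

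- Reviewed: 6 with and 14 without a complication. Confirmed: 6 × 0.8 = 4.8 and 14 × 0.4 = 5.6.
- Not reviewed: 60 × 0.3 = 18 with and 42 without a complication.
- AKI group: 18 + 4.8 = 22.8 with and 42 + 5.6 = 47.6 without, total 70.4. Complication rate 22.8 / 70.4 = 32.4%.
- Non-AKI group: 105 − 22.8 = 82.2 with and 245 − 47.6 = 197.4 without, total 279.6. Complication rate 82.2 / 279.6 = 29.4%.
- Odds ratio: (22.8 × 197.4) / (47.6 × 82.2) = 1.15.
- Chance of p < 0.05 with no true association (two-proportion normal approximation, two-sided): about 8% instead of 5%.

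**How it moves with the number reviewed and the confirmation gap.** Same cohort:

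| Suspected cases reviewed | Confirmed, with v without complication | Odds ratio | False-positive rate |
|---|---|---|---|
| 10% | 90% v 70% | 1.03 | 5.2% |
| 10% | 95% v 60% | 1.05 | 5.4% |
| 25% | 90% v 70% | 1.07 | 5.8% |
| 25% | 95% v 60% | 1.13 | 7.4% |
| 100% | 90% v 70% | 1.36 | 18.7% |
| 100% | 95% v 60% | 1.75 | 46.5% |
| any of these | 80% v 80% | 1.00 | 5.0% |

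The last row is a review that does not depend on outcome: the bias vanishes however many cases are reviewed. If reviewers leaned the other way, the odds ratio would fall below 1.

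**The case against.** The strongest reply is that hardly anyone may reach the review. These are elective patients, the CRF has a preoperative creatinine field, and baseline may come from any value in the previous 90 days. The exclusion criteria also remove patients whose creatinine or urine output is missing for the AKI definition. If that covers a missing baseline, the reviewed group is empty. This stands, and it is why the effect is probably small.

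A second reply is that confirming the diagnosis may only mean checking the case against the numeric rule just given, and that the urine-output criterion needs no baseline. That is possible, but the text does not say so. A check against a rise from baseline is also not straightforward when no baseline exists.

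A third is that silence about masking does not prove that outcomes are seen. This also stands. The documents do not describe the reviewer or the material used, and the CRF has no field for the review decision. Access to outcomes is inferred from the retrospective design and the shared CRF.

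Two stronger readings are tempting and are not supported. A reader might infer that the associations will be inflated; the documents fix neither the direction nor the size. A reader might also compare confirmed with refuted cases among the 20 reviewed, which under the same assumptions gives 4.8 / 10.4 = 46% against 1.2 / 9.6 = 12.5%. No such comparison is planned. The statistical analysis section compares all AKI with all non-AKI patients, where the gap is 32.4% against 29.4%.

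**Conclusion.** The point holds in a limited form. For patients without a baseline creatinine, the AKI label rests on a judgement that the plan does not restrict to renal data, in a setting where outcomes are already known and recorded on the same form. That leaves room for outcome-dependent labelling in the association endpoints. The primary incidence also depends on this discretion, though not through an association.

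The odds ratio of about 1.15 rests on the assumed 350 patients, 80 suspected and 20 reviewed cases, 30% complications, and a twofold gap in confirmation that nothing in the documents establishes. With one in ten suspected cases reviewed, the tabulated odds ratios are at most 1.05. The larger values, 1.36 and 1.75, need the less natural reading that every suspected case is reviewed. The change is worth making because it costs little and because the number of reviewed patients is unknown, not because a large bias has been shown.

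**What to change.** In the section on assessment of renal function:

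- State which cases are reviewed, and whether the exclusion for missing creatinine covers a missing baseline.
- Confirm AKI against the stated criteria, using only creatinine, urine output, weight and fluid balance up to the end of the AKI window. Define that window for this route, since the screen covers the whole stay and the primary endpoint 48 hours. If a later creatinine may serve as the reference value, say which.
- Record and lock the decision before the outcome pages are completed for that patient.
- Add a CRF variable that flags patients classified by this route.

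In the statistical analysis section, report how many patients were flagged, and repeat the incidence estimate and the AKI-complication comparisons without them.

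The cost is one variable, one extra analysis and slightly slower abstraction. Locking will not fully mask someone who has already read the whole chart, and a renal series that stops early can itself reveal a death. The repeat analysis is therefore needed as well as the lock. If the review has already taken place, as the past tense may suggest, the flag and the repeat analysis can still be done.

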## **PRIMARY ENDPOINTS**

- To evaluate the incidence of postoperative AKI according to KDIGO criteria within 48 hours after surgery

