## **SECONDARY ENDPOINTS**

- Distinction between transient and persistent AKI
- Occurrence of recovery or progression at 7 days, 30 days and 3 months
- Association between AKI and pulmonary complications, major adverse cardiovascular events, anastomotic or septic complications, or death.
- Identify risk factors associated with AKI occurrence.

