## **STATISTICAL ANALYSIS**

The statistical analysis will be conducted with the help of Spss software.

Continuous variables are presented through descriptive statistics, including mean, median, variance, minimum and maximum value. Categorical variables are described by the absolute frequencies and percentages.

Data will be examined by T-test or one-way ANOVA (normally distributed variable), Mann-Whitney U test, Kruskal-Wallis one way analysis test (not normally distributed variables), Pearson or Mc Nemar's chi-square test (categorical variables) will be used to evaluate the difference across non-AKI group versus AKI group according to KDIGO criteria or each type of AKI. Two-sided p-values of less than 0,05 were accepted as statistically significant.

Logistic regression analysis will used to build a model of covariates associated with development of AKI and risk of AKI. Likelihood ratio (LR) test statistic, Hosmer-Lemeshow (HL) statistic will used

for assessing goodness of fit (GOF) in the regression models. A discriminatory performance [DP] assessment of the binary logistic model will be performed by classification/diagnostic table, ROC and area under the curve (AUC).

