**INTRAOP DATA**

Type of surgery:  thoracoscopy  thoracotomy  vls  lpt  cervico

Type of anesthesia:

inhaled  TIVA  epidural+inhaled  epidural+TIVA  
 Lidocaine \_\_\_\_mg  Magnesium\_\_\_\_\_mg  Dexamethasone \_\_\_\_\_mg  
 Ranitidine\_\_\_\_\_mg  PPI \_\_\_\_\_mg

NMB:  rocuronium  cisatracurium

NMB reversal:  neostigmine  sugammadex

Duration of anesthesia: \_\_\_\_\_ h

Type of ventilation:  OLV  TLV max FiO2\_\_\_\_\_ min SpO2\_\_\_\_\_

Hemodynamics:

IABP min SBP\_\_\_\_\_mmHg

fluids:  crystalloids\_\_\_\_\_ml  colloids\_\_\_\_\_ml  
 blood\_\_\_\_\_ml

blood loss\_\_\_\_\_ml end\_surgery Hb\_\_\_\_\_ end\_surgery lactate\_\_\_\_\_

use of vasopressors  max dose\_\_\_\_\_

use of inotropes  max dose\_\_\_\_\_

arrhythmia during surgery  use of antiarrhythmics

Diuresis: total \_\_\_\_\_ml  use of diuretics: \_\_\_\_\_ dose\_\_\_\_\_

End-surgery medication:  NSAIDs

Extubation at the end of surgery  PACU  ICU

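### Adjusted creatinine puts fluid balance and weight inside the AKI outcome, and no result on measured creatinine is planned, so a fluid association (and, weakly, a weight one) can be partly definitional

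*Combined protocol and SAP*

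**What the plan says.** The primary endpoint is "To evaluate the incidence of postoperative AKI according to KDIGO criteria within 48 hours after surgery". Under Assessment of renal function, AKI is a creatinine rise of at least 0.3 mg/dL from a baseline taken from records of the previous 90 days, or a urine output below 0.5 mL/kg/h for 6 hours. The same section adds: "Positive fluid balance and hemodilution are considered in the diagnosis and staging of AKI using the following formula". The correction factor is built from "weight (kg) upon hospital admission" times 0.6 and a sum of fluid balances in litres. It is described for the creatinine used in diagnosis and staging; nothing is said about correcting the baseline.

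A secondary endpoint is "Identify risk factors associated with AKI occurrence". The Statistical Analysis section compares patients with and without AKI and adds: "Logistic regression analysis will used to build a model of covariates associated with development of AKI and risk of AKI". It lists no covariates and excludes none. The Sample Size section plans for 8 covariates.

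The case report form records weight before surgery; "crystalloids", colloids, blood, blood loss and diuresis during surgery; and fluids in, diuresis and drainages afterwards. No section plans an incidence or a model on measured creatinine.

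**The concern.** Two patients with the same baseline and the same measured postoperative creatinine can be classified differently because one has a larger recorded fluid balance or a lower weight. If either variable is then examined as a correlate of AKI, part of the association is already in the outcome.

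The correction removes a bias if the recorded balance really dilutes creatinine by the amount the formula assumes, and adds one if it does not. Some over-correction is plausible from the form itself: the only outputs recorded are diuresis, drainages and blood loss, so insensible losses stay in the balance. With only the adjusted version reported, a reader cannot separate a kidney effect of fluid from the correction, or see how much of the primary incidence comes from it.

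**Working it through.** **The plan's own figure.** 8 events per covariate × 8 covariates = 64 events, as stated in Sample Size. At the 18.3% incidence of one study cited in the Introduction, 64/0.183 gives about 350 patients, the size used in step 4.

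**1. The factor.** With the denominator bracketed and net balance counted once,

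factor = (0.6 × weight + balance)/(0.6 × weight) = 1 + balance/(0.6 × weight).

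For a balance of +4 L: 1 + 4/30 = 1.133 at 50 kg, 1 + 4/42 = 1.095 at 70 kg, and 1 + 4/54 = 1.074 at 90 kg.

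**2. Who is reclassified.** The balance that carries a measured value to the threshold is 0.6 × weight × [(baseline + 0.3)/(baseline + measured rise) − 1]. For a baseline of 1.0 mg/dL and a measured rise of 0.2 (not AKI), at 70 kg: 42 × (1.3/1.2 − 1) = 3.5 L. The figures are 2.5 L at 50 kg and 4.5 L at 90 kg. With no measured rise they are 9.0, 12.6 and 16.2 L at 50, 70 and 90 kg. The correction therefore acts mainly on patients near the threshold.

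**3. Size with no true fluid effect.** The documents give no patient values, so these are assumed: baseline 0.9 (SD 0.18) mg/dL, true change 0.05 (SD 0.20) mg/dL unrelated to fluid or weight, net balance 3 (SD 1.5) L, weight 70 (SD 13) kg. AKI is a rise of at least 0.3 mg/dL over the uncorrected baseline. The share of the recorded balance that dilutes creatinine is unknown and was varied. The simulation used 400,000 patients; repeat runs move the odds ratios by 0.01 to 0.02.

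| Share that dilutes | Incidence, measured | Incidence, adjusted | OR per litre, measured | OR per litre, adjusted |
|---|---|---|---|---|
| None | about 11% | about 20% | 0.99 | 1.24 |
| Half | about 7% | about 15% | 0.87 | 1.12 |
| All | about 5% | about 11% | 0.74 | 1.00 |

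Restricting the correction to positive balances left these essentially unchanged. The adjusted odds ratio for weight is about 0.90 per 10 kg with no dilution and closer to 1 otherwise.

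**4. What a study of this size would report.** Here 1,000 replicates of 350 patients were run under slightly different assumptions (balance SD 1.7 L, baseline SD 0.2, change 0.02 with SD 0.22 mg/dL), with fluid balance and weight in the model at the plan's two-sided 0.05. With adjusted creatinine and no true effect, fluid balance was significant in 69%, 22% and 4% of replicates with none, half and all of the balance diluting. Weight was significant in 14%, 6% and 5%. With measured creatinine, fluid was significant in 5.5% with no dilution, but in 17% with half and 48% with full dilution, in the protective direction.

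**5. A literal reading.** If daily cumulative balances are summed as written, early fluid is counted more than once. Taking day 1 as 60% of the 48-hour balance, fluid was then significant in 26% of replicates even with full dilution.

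**The case against.** The correction is a referenced method aimed at a real problem. Where dilution is complete, the adjusted version is the unbiased one (1.00) and measured creatinine misleads (0.74). At half dilution the two err by similar amounts in opposite directions. All of this stands, and it is why the correction should stay and be shown beside the measured result.

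A reader might infer more than the documents support:

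- **That fluids and weight are declared candidate risk factors.** They are fields on the case report form, and no covariate is named. Weight is needed anyway for the urine criterion and the correction. The artefact arises only if an open-ended comparison or model takes these fields up.
- **That the adjusted incidence is about double the true one, or that the odds ratio of 1.24 is expected.** That reading needs none of the recorded balance to dilute creatinine, which is the extreme case.
- **That these figures describe all AKI.** They cover the creatinine route only. If 20% or 40% of patients met the urine criterion independently of fluid (assumed), the worst-case odds ratio falls from 1.25 to 1.14 or 1.09, and the half-dilution one from 1.12 to 1.06 or 1.04. Low urine output also raises net balance, a separate link that was not modelled.
- **That the odds ratio per litre applies to intraoperative crystalloids, colloids or blood.** The simulated exposure is net balance. The documents do not say when the balance starts, so intraoperative volumes are affected only as far as they enter it.
- **That low weight will appear as a risk factor.** That artefact is weak.

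**Conclusion.** The point holds as a gap in reporting and interpretation. By algebra, the AKI outcome contains fluid balance and admission weight, and nothing planned shows the result without them. Under the stated assumptions and for creatinine-defined AKI, the definitional part of the odds ratio per litre of net balance lies between about 1.24 and 1.00 on the adjusted version. The opposite artefact on the measured version lies between 0.99 and 0.74. The gap in incidence is about 6 to 9 percentage points (11 − 5 = 6; 20 − 11 = 9) and would be smaller once AKI met by urine output is counted.

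Where the study falls in these ranges depends on how much of the recorded balance dilutes creatinine, which the documents do not allow anyone to determine. The documents therefore do not show that the correction is wrong, or that a fluid finding would be spurious. They show that the adjusted version alone could not settle the question.

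**What to change.** - **Primary Endpoints and Assessment of renal function:** report the 48-hour AKI incidence with measured and with adjusted creatinine side by side.
- **Statistical Analysis:** repeat the AKI comparison and the logistic model with AKI defined on measured creatinine. For any fluid or weight variable, show both odds ratios with confidence intervals.
- **Interpretation:** state that cumulative fluid balance is a component of the adjusted outcome, so that an association on the adjusted version alone is not read as an independent risk factor.

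A rule that accepts fluid as a risk factor only when both versions point the same way is not recommended. With no dilution the measured odds ratio is close to 1, so its direction is near chance. At 350 patients with no true effect, such a rule still passed a spurious fluid finding in about 43% to 46% of replicates, against 67% without it. With full dilution and a real effect (adjusted odds ratio 1.21), it cut detection from 32% to 17%.

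The cost is one extra incidence figure and one repeated analysis on data already collected. A finding on fluid or weight may have to be stated less firmly.

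### The hemodilution correction factor has no brackets around its denominator; computed as printed, it is 0.36 times the evidently intended value

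*Combined protocol and SAP*

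**What the plan says.** The Primary Endpoints section states the aim: "To evaluate the incidence of postoperative AKI according to KDIGO criteria within 48 hours after surgery". The section Assessment of renal function defines AKI by a rise in SCr of at least 0.3 mg/dL within 48 h, or by urine output below 0.5 mL/kg/h for 6 h.

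The same section then brings in hemodilution: "Positive fluid balance and hemodilution are considered in the diagnosis and staging of AKI using the following formula". Adjusted SCr is SCr times a correction factor. The line defining the factor begins "where the correction factor = (weight (kg) upon hospital admission", multiplies that weight by 0.6, adds the summed fluid balance and closes the outer bracket. It continues "daily cumulative fluid balance (L)))/hospital admission weight" and ends with a multiplication by 0.6. No bracket encloses the weight and the 0.6 that follow the slash.

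The formula appears nowhere else in the document. There is no worked example and no stated numerical value of the factor.

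**The concern.** A correction for positive balance and hemodilution should leave SCr unchanged when the balance is zero and raise it when the balance is positive. The printed line, evaluated by normal operator order, divides by weight and then multiplies by 0.6. It therefore lowers SCr at any plausible balance, which is the opposite of its stated purpose.

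The formula is to be used in diagnosing and staging AKI, so it bears on the creatinine part of the primary incidence. It also bears on what depends on AKI status: the comparison of patients with and without AKI, the logistic model, the split into transient and persistent AKI, and acute kidney disease. If the line were typed as printed into the analysis software, creatinine-based AKI would be under-detected wherever the adjusted value decides the diagnosis.

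**Working it through.** The plan gives no value of the factor, so there is no figure to reproduce. The check is algebra, followed by illustration.

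**Inputs from the protocol (Assessment of renal function).** The coefficient 0.6, the printed order of operations, and the SCr criterion of 0.3 mg/dL.

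**Assumed for illustration (not in the protocol).** Weights of 50, 70 and 90 kg, balances of 0, 3 and 5 L, and a baseline SCr of 1.0 mg/dL.

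**Step 1: the two readings.** W is admission weight (kg) and B is summed balance (L).

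- As printed: (0.6W + B)/W × 0.6 = 0.36 + 0.6B/W
- Denominator bracketed: (0.6W + B)/(0.6W) = 1 + B/(0.6W)
- Printed divided by bracketed: 0.6 × 0.6 = 0.36, whatever W and B are

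**Step 2: which reading fits the purpose.** At B = 0 the printed form gives 0.36 and the bracketed form gives 1. For the printed factor to reach 1, B must equal (1 − 0.36)W/0.6. At 70 kg that is 0.64 × 70/0.6 = 74.7 L. Only the bracketed form behaves as a correction for positive balance.

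**Step 3: measured SCr needed to meet the creatinine criterion.** With the baseline of 1.0 mg/dL left as measured, the threshold is 1.30/factor.

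| W (kg) | B (L) | Factor, printed | Factor, bracketed | Threshold, printed (mg/dL) | Threshold, bracketed (mg/dL) |
|---|---|---|---|---|---|
| any | 0 | 0.360 | 1.000 | 3.61 | 1.30 |
| 70 | 3 | 0.386 | 1.071 | 3.37 | 1.21 |
| 50 | 5 | 0.420 | 1.167 | 3.10 | 1.11 |
| 70 | 5 | 0.403 | 1.119 | 3.23 | 1.16 |
| 90 | 5 | 0.393 | 1.093 | 3.31 | 1.19 |

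**Step 4: if the baseline is also multiplied by the printed 0.36.** The threshold becomes (0.36 + 0.30)/factor.

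- Zero balance: 0.66/0.36 = 1.83, against 1.30 bracketed, a gap of 0.53 mg/dL.
- 50 kg and +5 L: 0.66/0.42 = 1.57, against 1.11 bracketed, a gap of 0.46 mg/dL.

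The distortion is smaller in this case, but in both examples it still works against detection.

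**The case against.** **The intention is plain.** The numerator repeats weight times 0.6, and the stated purpose admits only one reading. No analyst faces a real choice between two definitions. A literal coding would also be conspicuous, because every adjusted SCr at zero balance would fall by 64%. The 100-patient pilot described under Sample Size gives an early chance to notice. This stands, and it is why the point is minor.

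**The layout may have been altered.** A stacked fraction flattened when the PDF was converted to text would need no brackets. That cannot be ruled out entirely. However, the outer bracket around the numerator and the explicit slash suggest a formula typed on one line, and a look at the source file settles it.

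**Literal coding is not shown.** Data Collection says "An electronic copy of CRF will be retained in Microsoft Excel format", and Statistical Analysis names SPSS. Neither section says where the factor is calculated, and the CRF laboratory grid has a field for SCr but none for adjusted SCr. This also stands: transcription as printed is a possibility that the documents neither confirm nor exclude.

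**Patients might still be flagged.** A reader might infer that affected patients would never reach the confirmatory step, described as "these suspected AKI were reviewed on a case-by-case basis to confirm the diagnosis". The text does not support that. It does not say whether screening uses measured or adjusted SCr. If measured values are used, patients are flagged as usual and an implausible adjusted value could surface at review. Patients without a baseline are also screened on a decrease of 0.3 mg/dL, so an artificially lowered value set against a measured one could flag them instead of hiding them.

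**Conclusion.** The formula is wrong as written. By normal operator order the factor is exactly 0.36 times the evidently intended one, and this does not depend on weight or balance. It is a notational slip in a rule that feeds the primary endpoint, so it deserves correction, but it is minor because the intended form is easy to recover.

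The threshold of 3.61 instead of 1.30 mg/dL rests on four conditions: the line is coded as printed, the baseline is 1.0 mg/dL and left as measured, the balance is zero, and adjusted SCr decides the diagnosis. If the formula is read as intended, there is no effect at all. The urine-output criterion is untouched in every case.

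A reader might go further and infer that the study's AKI incidence is, or will be, understated. The documents do not support this. They do not show how the factor is implemented, and they give no SCr or fluid-balance data from which a change in incidence could be estimated.

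**What to change.** Write the definition with both parts bracketed:

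correction factor = (hospital admission weight × 0.6 + B) / (hospital admission weight × 0.6)

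where B is the net cumulative fluid balance in litres up to the time of that SCr. In the analysis code, check that B = 0 returns exactly 1.

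The cost is one pair of brackets, one defining sentence and one line of code checking. The AKI criteria, the group comparisons and the logistic model do not change. If adjusted values have already been calculated, the same check on that file shows whether any need to be recomputed.
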